## **Informational patient brochure/Compliance Surveys/ Baseline and Follow-up KOOS and IKDC surveys/Clinical Assessments**

An informational brochure (see attached) will be used to assist in the recruitment of eligible patients. The brochure will describe the autologous platelet rich plasma treatment, process, risks, appointment information and post procedure information.

Patients randomized to the PRP Treatment arm will receive a Pre and Post-Injection Instruction handout (see attached). The handout describes how the patient should prepare for the PRP injections and what to expect after the injection.

The study personnel who consents the patient will request the patient's and parent's email addresses which will be used to send out the weekly and monthly surveys.

For the first 6 weeks of the study, all patients will receive a weekly Compliance Survey (see attached) created by the Sports Medicine physicians to validate compliance with 1. non-weight bearing, 2. wearing a brace, 3. at home PT exercises, and 4. no high impact activity.

**KOOS/IKDC surveys:** All patients will receive a baseline survey and repeat surveys at 6 wks, 12 wks, 6 m, 9m, and 12 months, which is considered standard of care, on the CHCO main campus or one of the following satellite locations (South, Parker, Centennial, Uptown/St Joseph's or Broomfield). The surveys will include the following outcome scales: Pedi IKDC and KOOS-child.

The Pedi-IKDC is a modified version of the widely used International Knee Documentation Committee (IKDC) Subjective Knee Form, which is a knee specific measure of symptoms, function and sports activity. The Pedi-IKDC was developed for use with children and adolescents ages 10-17. The reliability and validity of the Pedi-IKDC has been demonstrated to be acceptable in young patients with a variety of knee disorders.

Similarly, the KOOS – child is a pediatric version of the Knee Injury and Osteoarthritis Outcome Score (KOOS). The KOOS-child score is subdivided and scored in five categories: Pain, Other Disease-Specific Symptoms, Activities of Daily Living Function (ADL), Sport and Recreation Function and Knee-related Quality of Life (QOL).

[http://www.actaorthop.org/sup\\_files/5292.pdf](http://www.actaorthop.org/sup_files/5292.pdf)

[http://www.sportsmed.org/uploadedFiles/Content/Medical\\_Professionals/Research/Grants/IKDC\\_Forms/Pedi-IKDC%20Form.pdf](http://www.sportsmed.org/uploadedFiles/Content/Medical_Professionals/Research/Grants/IKDC_Forms/Pedi-IKDC%20Form.pdf)

Clinical follow up will also be performed following injections or the commencement of conservative therapy at 6 weeks, 12 weeks, 6 months, 9 months, and 12 months by [name]/[name] or their colleagues on the CHCO main campus or one of the following satellite locations (South, Parker, Centennial, Uptown/St Joseph's or Broomfield). The clinical findings documented will include presence or absence of a joint effusion, overall range of motion, presence or absence of joint line tenderness and positive or negative Wilson's test 6 week follow up for both groups will also include radiographic evaluation, which is standard of care. If

the patient is clinically or radiographically improving, physical therapy will be started as standard of care, following the same treatment protocol initially with closed kinetic chain, non-impact exercises. Patients will then slowly return to impact activities as tolerated over 3 to 4 months.

A patient Timeline of Activity has been created for each arm of the study (see two attachments). The Timeline describes the weekly and monthly events that will occur during this study and can be handed to the patient following the consent and randomization process.

### **6 month Research MRIs**

- If the patient received their initial diagnostic MRI by a Non-contrast MRI, the patient will receive a Non-contrast MRI at their 6 month research MRI visit.
- If the patient received their initial diagnostic MRI by a dGEMRIC MRI, the patient will receive a dGEMRIC MRI at their 6 month research MRI visit.
- If the patient received their initial diagnostic MRI by a MRI with and without contrast, the patient will receive a Non-contrast MRI at their 6 month research MRI visit.

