#### **Patient Recruitment**

A diagnostic knee MRI (through CHCO or an outside facility) will have been performed as standard of care prior to study participation, utilizing dGEMRIC, a Non-contrast MRI or a MRI with and without contrast in patients with a high clinical suspicion for osteochondritis dissecans. The study is posted on the clinicaltrials.gov website and patients and/or their parents may call and inquire about eligibility.

Lesions will be classified according to Di Paola et al classification [33]

This uses 5 stages as follows:

Grade 1: Small change of signal without clear margins of fragment,

Grade 2: osteochondral fragment with clear margins but without fluid between fragment and underlying bone,

Grade 3: fluid is visible partially between fragment and underlying bone,

Grade 4: fluid is completely surrounding the fragment, but the fragment is still in situ;

Grade 5: fragment is completely detached and displaced.

Only patients with Di Paola stage 1 or 2 lesions will be approached for study participation and consented into the study.

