### **Exclusion criteria**

1. Patients with polyarticular disease (not applicable to polyarticular disease of the knees as the most symptomatic knee will qualify for the study)
2. Patients with blood disorders (Blood disorders (thrombopathy, thrombocytopenia, anemia with hemoglobin <9g/dL).
3. Patients who had intra-articular treatment with steroids within 3 months
4. Patients who are pregnant or nursing at the time of consent.
5. Patients with inflammatory arthritic conditions (e.g. rheumatoid arthritis)
6. Non-English speaking patients. (Scores used for evaluation have not been validated in Spanish)
7. Patients who had previous knee surgery
8. Additional disabilities in any of the lower limbs that would interfere with any of the clinical assessments.
9. Chronic use of NSAID (defined as taking NSAID regularly every week for the last 6 months), steroids or chemotherapy drugs
10. Treatment with NSAIDs within 15 days prior to randomization in this study
11. Patients with a BMI over 30. Due to the fact that this study utilizes an injection technique which may be inaccurate in obese subjects.
12. Patients with a contraindication to MRI including: patients with cardiac pacemaker or non-approved intracranial vascular clip, and those with orthopedic hardware as the resulting artifact can complicate interpretation
13. Patients with acute or chronic renal failure
14. Patients with a previous anaphylactic reaction to gadolinium enhanced MRI.
15. Patients with Di Paola stage 3 or 4 lesions
16. Patients who received a MRI diagnosis of OCD but do not have the specific cartilage imaging sequences.
17. Clinical or laboratory evidence of septicemia

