### **Proposed statistical analysis for Aim 1: Cartilage healing**

The T1GD value on dGEMRIC measures GAG content in cartilage. Higher T1GD values are associated with higher GAG content in the tissue, a positive measure of cartilage health. We assume that the value is approximately normal.

We plan to fit a general linear mixed model [39] for the outcome of T1GD. Predictors will include the visit at which the T1GD test was performed (initial MRI and 6 months), whether the site was weight bearing or not, and whether the side was affected or not, and the treatment group. Age will be included as a covariate. An unstructured covariance will be used to account for correlation between T1GD measurements on the same participant. Jackknifed-studentized residuals will be examined to assess normality, and transformations will be applied as appropriate.

We will test the null hypothesis of no time by treatment by weight bearing surface by affected side interaction. Given a non-significant interaction, we will test the main effects of time and treatment, comparing the difference between the weight-bearing and non-weight bearing surface for the affected and non-affected sides. Estimates, 95% confidence intervals, and p-values will be produced. All hypothesis tests will be performed using the Wald test with Kenward and Roger degrees of freedom[40] . Hypothesis tests will be performed at the Bonferroni corrected alpha of  $0.05/3 = 0.017$ .

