### **Proposed statistical analysis for Aim 2: Functional Recovery and Symptoms**

We will analyze scores for each subscale of the KOOS-child, and the overall score produced by the pedi-IKDC range from 0 to 100, with higher scores indicating improved knee function. Each measure is approximately normal.

We describe the analysis for Aim 2, Sub-aim 2.1. The analyses for the other sub-aims are exactly parallel.

We plan to fit a general linear mixed model [39] with the pain subscale of the KOOS-child as the outcome. Predictors will include the visit at which the survey was given (6 weeks, 12 weeks, 6 months, 9 months and 12 months) and treatment group. Age will be included as a covariate. An unstructured covariance will be used to account for correlation between measurements on a single participant. If the resulting model fails to converge, a spatial exponential covariance will be used. Jackknifed-studentized residuals will be examined to assess normality, and transformations will be applied as appropriate.

We will test the null hypothesis of no polynomial time trend by treatment interaction. If the time-by-treatment test is non-significant, we will step down to test the main effects of time and treatment. Estimates, 95% confidence intervals, and p-values will be produced.

All hypothesis tests will be performed using the Wald test with Kenward and Roger degrees of freedom [40] . Three hypothesis tests may be performed for each outcome, for a total of 12 tests. To control for multiple comparisons, all hypotheses will be tested at the Bonferroni corrected alpha level of  $0.05/12=0.004$ .

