### **Power Analysis**

We conducted a power analysis for Aim 1, the primary endpoint of the study. The maximum sample size for the proposed trial is fixed at 12 patients per arm (24 participants total). The sample size is limited due to costs associated with dGEMRIC.

We calculated power for the test of no difference in T1GD between the treatment groups. We assumed a standard deviation of 50 ms for T1GD values, and a correlation of 0.2 between the baseline MRI and the 12-month T1GD measurements. Estimates were based on T1GD values reported by Neuman et al[42]. We expect T1GD values to be 85 ms higher in the injection group when compared to conservative therapy at the 6 month time point with no difference at baseline. We calculated power for 10, 11, or 12 participants per arm. Power was calculated using GLIMMPSE version 2.0.1.[43]

To detect a mean difference of 85 ms in T1GD between the treatment groups, power will be 0.93 with a Type I error rate of 0.05, for 12 participants per treatment group. To ensure a conclusive study, we will target an effective sample size of 10 participants per group. Over the 12 months, we expect to lose up to two participants per treatment group. To account for the attrition, we have set an enrollment goal of 24 participants, or 12 participants per treatment group.

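### T1GD will exist only for patients diagnosed by dGEMRIC, but the Aim 1 model and power treat it as available for all, and the Di Paola alternative has no specified between-arm test

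*Combined protocol and SAP*

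**What the plan says.** All references are to the combined protocol and SAP.

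- **Entry.** Under Patient Recruitment, the diagnostic scan may be done "utilizing dGEMRIC, a Non-contrast MRI or a MRI with and without contrast". Exclusion criterion 16 removes "Patients who received a MRI diagnosis of OCD but do not have the specific cartilage imaging sequences". It asks for cartilage sequences and does not ask for dGEMRIC.
- **Follow-up scan.** The section 6 month Research MRIs matches follow-up to diagnosis: "If the patient received their initial diagnostic MRI by a Non-contrast MRI, the patient will receive a Non-contrast MRI" at 6 months. Diagnosis by MRI with and without contrast also leads to a non-contrast scan. Only diagnosis by dGEMRIC leads to a 6-month dGEMRIC.
- **Aim 1 analysis.** "We plan to fit a general linear mixed model [39] for the outcome of T1GD". No other outcome is modelled for this aim. On the covariance: "An unstructured covariance will be used to account for correlation between T1GD measurements on the same participant".
- **Power Analysis.** Aim 1 is called the primary endpoint. Power is 0.93 for 12 per arm with T1GD. "The sample size is limited due to costs associated with dGEMRIC". The only margin is for loss to follow-up: "To account for the attrition, we have set an enrollment goal of 24 participants, or 12 participants per treatment group".
- **Di Paola.** Specific Aims, Research Methods and the closing summary of knowledge to be gained all give it as the alternative measure of cartilage healing. The section on the research MRI and the opening of the Data Analysis Plan provide for grading before and after treatment. The only hypothesis that mentions it is in Aim 3, an association with functional scores, in models that have T1GD as outcome.

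**The concern.** A patient who enters on a non-contrast scan, or on an MRI with and without contrast, has no planned T1GD at either visit. This differs from ordinary missing data, where a mixed model can still use the visits that were observed. Here the model has no outcome at all for the patient, even if the patient completes every visit.

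Three things follow. The primary analysis applies to a subset of the randomised patients that the plan neither names nor sizes. The stated power applies to that analysis only if every patient has dGEMRIC. And because Aim 1 offers two measures but specifies a test for one, it stays open until the results are known which measure carries the conclusion, and how the other patients contribute.

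**Working it through.** **Inputs (Power Analysis).** Difference 85 ms at 6 months and none at baseline; SD 50 ms; correlation 0.2 between visits; 12 per arm; Type I error 0.05, sidedness not stated. The Aim 1 analysis section uses 0.05/3 = 0.017.

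**Method.** Two-sample noncentral t with n dGEMRIC pairs per arm:

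- noncentrality = 85 / (SD × √(2/n)), with df = 2n − 2;
- 6-month value: SD = 50;
- change from baseline: SD = 50 × √(2 × (1 − 0.2)) = 63.25.

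**The plan's own figure.** At n = 12, the noncentrality is 85 / (50 × √(2/12)) = 4.16 for the 6-month value and 85 / (63.25 × √(2/12)) = 3.29 for change. The four variants give 0.978 (6-month, two-sided 0.05), 0.932 (6-month, two-sided 0.05/3), 0.882 (change, two-sided 0.05) and 0.939 (change, one-sided 0.05). The second and fourth come close to 0.93. The documents do not settle which was used, but every variant needs T1GD on all 12 per arm.

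**Fewer pairs.** The dGEMRIC share is not in the documents, so the rows are assumed numbers of patients per arm with T1GD at both visits, equal in the two arms.

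| Pairs per arm | 6-month, two-sided 0.05 | 6-month, two-sided 0.05/3 | Change, two-sided 0.05 | Change, one-sided 0.05 |
|---|---|---|---|---|
| 12 | 0.98 | 0.93 | 0.88 | 0.94 |
| 10 | 0.95 | 0.86 | 0.81 | 0.89 |
| 8 | 0.89 | 0.74 | 0.71 | 0.82 |
| 6 | 0.76 | 0.55 | 0.56 | 0.70 |
| 4 | 0.52 | 0.30 | 0.36 | 0.52 |

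The smallest number of pairs per arm that gives 0.80 is 7, 9, 10 and 8 respectively. These are proxies. None is the four-way interaction test that the Aim 1 section plans to do first.

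**Who enters which analysis, as written.**

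| Diagnostic scan | 6-month scan | T1GD | Enters the Aim 1 model | Between-arm test of Di Paola |
|---|---|---|---|---|
| dGEMRIC | dGEMRIC | both visits | yes | none specified |
| Non-contrast | Non-contrast | none | no | none specified |
| With and without contrast | Non-contrast | none planned | no | none specified |

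**Side note on fitting the model.** Four sites at two visits make eight T1GD values per patient. Read as one 8 × 8 unstructured matrix, the covariance has 8 × 9 / 2 = 36 parameters. With 10 patients in two arms, 10 − 2 = 8 residual degrees of freedom remain for eight measures. The common age slope can then be chosen so that the residual matrix is singular, and the REML likelihood has no finite maximum. The same holds for fewer than 10 patients. In simulated data, fits degenerated at 8, 9 and 10 patients and converged at 11, 12 and 24. The Aim 1 section names no fallback, whereas Aim 2 does: "If the resulting model fails to converge, a spatial exponential covariance will be used".

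**The case against.** **The Di Paola comparison is planned.** A reader might infer that these patients' endpoint is never compared between arms. The documents do not support that. Specific Aims, Research Methods and the closing summary all frame Di Paola change within the comparison with conservative therapy. What is missing is its test, model and alpha.

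**The power loss is not shown.** This stands. The section on the research MRI says that each patient has four T1GD values at both visits, the footnote to Table 3 speaks of the same standard MRI procedure for all, and cost of dGEMRIC is given as the limit on sample size. All three fit an expectation that most or all patients would have dGEMRIC. At a high share the loss is modest: on the 6-month value at two-sided 0.05, 7 pairs per arm still give 0.83. But nothing in the eligibility criteria secures a high share, and no minimum number is set. The sentence about each patient may mean each dGEMRIC patient; either way it has to be reconciled with the scan-matching rule.

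**Attrition should not be counted in full.** This also stands. The loss of two per arm is expected over 12 months, while the scan is at 6 months. The table is therefore given by number of pairs and not tied to a share of 10 completers per arm.

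**Bias by arm.** A reader might infer that the dGEMRIC subset is distorted by treatment. The type of scan is fixed before assignment, so it cannot itself depend on arm. Nor can the subset be called free of bias, since patients may leave after seeing an open-label assignment.

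**The covariance limit depends on one reading** of the matrix and on 10 or fewer dGEMRIC patients. It is secondary and does not carry the point.

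**Conclusion.** The gap is real and rests on explicit text. T1GD is obtained only in patients diagnosed by dGEMRIC, the specified Aim 1 model and its power use T1GD alone, and the alternative measure has no specified between-arm analysis. Following the plan leaves some randomised patients out of the primary analysis, unless every enrolled patient happens to have been diagnosed by dGEMRIC.

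The size is conditional. With 8 pairs per arm, power is 0.71 to 0.89 across the four proxies; with 6 it is 0.55 to 0.76; with 4 it is 0.30 to 0.52. These figures assume the plan's 85 ms, SD 50 ms and correlation 0.2, and equal pairs per arm. The Randomization section describes no stratification by scan type, so equal numbers are not assured. To say that the trial is underpowered would go beyond the documents, because they do not give the dGEMRIC share. The gap in the primary analysis does not depend on that share being low and should be closed before unblinding.

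**What to change.** 1. **T1GD.** State that T1GD is analysed in the dGEMRIC subset. Reconcile the section 6 month Research MRIs with the statement that each patient has T1GD at both visits. Restate the power for the number of dGEMRIC pairs expected at 6 months, giving the contrast, sidedness and alpha.
2. **Di Paola.** Confirm that the grading before and after treatment in the Data Analysis Plan applies to all patients, and name the graders, since the two radiologists are named only for the T1 values. Add a between-arm comparison of the 6-month grade in all randomised patients with a 6-month scan, for example an exact or ordinal test that accounts for baseline grade.
3. **Primary analysis.** Before unblinding, name which analysis is primary for Aim 1 and how its alpha is used. If T1GD stays primary, say that the result applies to the dGEMRIC subset.
4. **Covariance.** Name a fallback for the Aim 1 model, as Aim 2 does.

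**Cost.** Wording and one added analysis, with no added scans. The stated T1GD power becomes less favourable unless all patients have dGEMRIC. The Di Paola comparison detects only large differences: an unstratified Fisher exact test at two-sided 0.05 with 12 per arm has power 0.61 if 80% versus 30% improve (assumed rates). It is lower if healing under conservative therapy is more common, for example 0.21 for 80% versus 50%.

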### **Research MRI utilizing dGEMRIC or Non-contrast MRI**

Once the intrarticular PRP injections have been administered, a follow-up MRI will be performed utilizing dGEMRIC or Non-contrast MRI at 6 months from the initial visit. Mean T1 values on dGEMRIC will be calculated by drawing a region of interest at the site of hyaline cartilage pathology, adjacent to the site of pathology within the hyaline cartilage, and distant to the site of pathology within the hyaline cartilage on initial and follow up imaging. If the follow-up imaging is with a Non-contrast MRI, the DiPaolo classification system will be used to quantify interval change.

Knee MRI with dGEMRIC will be performed in the standard manner. Upon arriving to the radiology department for the MRI, a pregnancy test will be administered for all female participants of child bearing potential. An institutional MRI screening form will be given to each patient and parent and reviewed with the MRI technologist. If there is any retained metal (pacemaker, metallic bb, orthopedic hardware), MRI will not be performed. If there is no contradiction to MRI based on the institutional screening form, the patient will have an IV placed. Using weight based dosing, .04 ml/kg, injection of gadolinium will be administered. The patient will then be asked to exercise for 30 minutes, which will be performed by walking around the hospital. The patient will then return to the MRI suite in the department of radiology. Standard screening for retained metal will be performed prior to entering the MRI scanning area. If the parent/guardian wishes to accompany the child for the MRI scan, they will be screened in identical fashion. In the MRI scanner, the patient will be required to lie still for approximately 1 hour, the duration of the scan. The patient will have the option of watching a

movie or listening to music on ipod or similar device (plugged in outside the scanner in technologist area) during imaging. No sedation will be given. There is no ionizing radiation associated with MRI.

Each patient will have four values of GAG (T1GD) measured at the baseline MRI and again at the 6 month MRI, via dGEMRIC. The locations of the measurements will be designated using the lateral view of the femoral condyle as a clock face with the medial femoral condyle superior location being designated as 12 o'clock, the inferior location being designated as 6 o'clock and the anterior location being designated as 3 o'clock; the lateral view of the femoral condyle as a clock face with the lateral femoral condyle superior location being designated as 12 o'clock, the inferior location being designated as 6 o'clock and the anterior location being designated as 9 o'clock. The values will be measured at four locations: the medial side at a weight bearing surface, the medial side at a non-weight bearing surface of the posterior condyle (4 o'clock), the lateral side at a weight bearing surface, and the lateral side at a non-weight bearing surface of the posterior condyle (8 o'clock). The side with the lesion will be designated as the affected side, and the side without the lesion will be designated as the non-affected side. GAG (T1GD) will be measured on the affected weight bearing surface at the site of the lesion. GAG (T1GD) will be measured on the non-affected side at the corresponding weight bearing surface of the femoral condyle.

